### **Subgroup analyses**

Rather than stratifying the analysis by subgroups, the intention is to extend the primary outcome analysis by including the main effect(s) and interaction terms for the variables listed below. These interactions will be exploratory and, to account for multiple testing, a false discovery rate adjustment will be made to p-values using the *p.adjust* function in R. Tests for variables with multiple categories will be reported at each level with 95% confidence intervals (CIs) with the inference based on an omnibus test across all levels.

- Ethnicity will be derived from self-reported pupil and staff survey data. Response options include broad ethnic classifications: Asian, Black, Mixed, White, Other, and Prefer not to say. These categories will be dummy coded with White as the reference category. They will then be integrated as interaction terms with group allocation, with pupil and staff categories incorporated into outcome models specific to each group.
- Pupil FSM eligibility will be obtained from local school administrative data in two waves: summer 2024 and summer 2025. This will be dummy coded (yes/no) and will be included as an interaction term with group allocation in pupil-specific outcome models.
- Pupil SEND/EHCP status will be obtained from local school administrative data. SEND/EHCP status will be a binary category, and pupils receiving any SEND support or who have an EHCP will be counted within the SEND/EHCP group. This will be dummy

coded (yes/no) and will be included as an interaction term with group allocation in pupil-specific outcome models.

We will also include a cross-level interaction between group allocation and scores on the staff-reported empathy and control sub-scales of the ARTIC 35 (Baker et al., 2021)

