## Analysis

Analyses will be conducted by an analyst masked to intervention group assignment following the intention-to-treat principle. The hypotheses and general analysis framework were decided a priori; the analysis plan was written and finalised during the period of data collection after recruitment but before baseline data collection was completed. The analyses will use maximum likelihood estimation meaning all participants will be included, even those with missing follow up data points, in line with the intention-to-treat principle. There will be two approaches to handling missing data, assuming that data are missing at random: 1) multiple imputation of data at any time point using wide format data, and 2) participants who have at least one post-randomisation observation will be included in the model with maximum likelihood estimation. Results will be compared using the two approaches. The chosen analysis model to assess the intervention effect is a mixed effects model. This model will form the basis of the main trial report that will be submitted for publication. Fixed effects will include group allocation (intervention/control), time (mid-programme/end of programme), and the interaction between group allocation and time. Random intercepts for pupils or staff nested within schools will also be specified, depending on whether the outcome is pupil- or staff-specific. The baseline level of the outcome will be included as a covariate to increase power and precision. Cohort (1/2), year group (8/9) and gender (dummy coded: male/female/gender diverse, reference: male) will be included as fixed effect prognostic factors to improve precision of the treatment effect. LA/CA was used as a stratifier in the randomisation, and it is intended to be included in the analysis as a fixed effect. However, there may be issues with model estimation due to a small number of schools per LA/CA (minimum of two). In this case, we will specify a three-level model (pupil, school, LA) or remove LA/CA as a fixed effect from the analysis. For the mixed effects models, the package *lme4* version (version 1.1-35.1) in R will be used (Bates et al., 2015). Interaction terms will be specified within the mixed effects models. Example syntax for the primary outcome of pupil externalising symptoms with LA/CA included as a fixed effect is:

```

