lmer(externalising ~ group * time + (1 + school | pupil) + baseline_externalising + cohort_1_2 + year_group_8_9 + male_female + male_diverse + LA_CA, data = MGDAS_data)
```

Subgroup analyses and further analyses are detailed in the relevant sections below.

Standard data quality checks will be performed in the data preparation stage before analysis, including impossible values, distribution of scores and residuals, outliers, low frequency categorical variables, linearity, and homogeneity of variance. Violations will be managed with

appropriate techniques. Descriptive statistics of the implementation data will be used to identify levels of implementation and engagement.

There are no planned interim analyses for efficacy.

This project contains multiple secondary outcomes and analyses. For pupils, there are 16 secondary outcomes, and, for staff, there are 7 secondary outcomes. As a result, there is a higher risk of false positives overall. To mitigate this, false discovery rate (FDR) multiple comparison correction will be applied to the significance level for tests for outcomes that are within the same measure, as these are likely to be correlated both theoretically and statistically. For example, FDR correction will be applied to three SDQ secondary pupil outcomes. In a similar vein, FDR correction will be applied to subgroup and further analyses. Some of these analyses will be underpowered, increasing the chance of false negatives in some cases. All exploratory analyses must therefore be treated with caution and not interpreted individually.

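### The pupil-level subgroup interactions (FSM, SEND/EHCP, ethnicity) have no school-level random slope, so their error rate can exceed 5% by an amount set by a variance the SAP does not give

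*SAP*

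**What the plan says.** The section Subgroup analyses builds each subgroup model on the primary one: "the intention is to extend the primary outcome analysis by including the main effect(s) and interaction terms for the variables listed below". FSM eligibility and SEND/EHCP status are each coded yes/no, and each "will be included as an interaction term with group allocation in pupil-specific outcome models". Pupil ethnicity has six categories with White as reference, "with the inference based on an omnibus test across all levels", and 95% intervals are reported at each level.

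The primary model's random part appears in three places. The text of the section Analysis states: "Random intercepts for pupils or staff nested within schools will also be specified". The example syntax there uses the term "1 + school | pupil", which groups by pupil. The equation under Primary outcome analysis carries an intercept for school and one for LA/CA. The three do not agree with one another, but none contains a school-level slope for a pupil characteristic, and the subgroup section adds none.

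On status, the SAP says: "These interactions will be exploratory and, to account for multiple testing, a false discovery rate adjustment will be made to p-values". The section Analysis adds: "All exploratory analyses must therefore be treated with caution and not interpreted individually".

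**The concern.** Schools are randomised and the moderators vary within schools. The group-by-FSM term therefore compares 31 school-specific FSM gaps in one arm with 31 in the other. A school intercept cancels out of a within-school gap. What remains in the planned model is pupil-level error only, which amounts to assuming that, within an arm, the true gap is the same in every school. If the gap differs between schools for reasons unrelated to training, that variation is missing from the standard error, and the test can reject although training works equally well in both subgroups.

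At stake are the p-values and the intervals at each level for statements on which pupils benefit. FDR adjustment takes p-values as valid input, so it carries the error through. The SAP discusses false positives only as a matter of multiplicity and warns that these analyses may be underpowered. A reader would not expect the tests to run above their nominal level.

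**Working it through.** **The SAP's own figure first.** At randomisation it uses 5.21 vs 4.7, SD 2.96, ICC 0.041, mean cluster size 219.73, CV 0.366, two-sided 5%, 80% power.

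- Individually randomised size per arm: 2 × (1.960 + 0.842)² × 2.96² / 0.51² = 528.8.
- Design effect: 1 + 218.73 × 0.041 = 9.968.
- Relative efficiency for unequal clusters: L = 219.73 × 0.041 / (219.73 × 0.041 + 0.959) = 0.904; 1 − 0.366² × 0.904 × 0.096 = 0.988.
- Result: 528.8 × 9.968 / 0.988 ≈ 5,333 pupils, or 24.27 schools per arm. Dividing by 0.85 gives 28.6, rounded up to 29 schools and 6,372 pupils. This matches the SAP's 24.3, 5333.02, 29 and 6372, so its inputs are read correctly here. The SAP states no error rate or power for the subgroup tests.

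**Inputs for the interaction.** From the SAP: 31 + 31 schools, about 220 pupils per school, CV 0.366, ICC 0.041; FSM about 28.4% (28.6% and 28.2% in Table 1), SEND/EHCP about 16% (15.6% and 16.5%), Mixed ethnicity about 4.5% (4.2% and 4.8%). Assumed, because the SAP does not give them: τ, the between-school SD of the subgroup gap in outcome-SD units, and the share of variance explained by baseline, taken as 0 to 0.5 (within-school variance σ² = 0.959 to 0.480). For scale, the school-intercept SD implied by the ICC is √0.041 = 0.20, and with Table 1's SD of about 4.23 a gap SD of 0.10 is 0.42 SDQ points.

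**Formula.** With equal school sizes, the true variance of the contrast divided by the variance the planned model reports is

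1 + τ² × m × p(1 − p) / σ²,

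and the actual size of a nominal 5% test is 2[1 − Φ(1.96 / √ratio)].

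FSM, τ = 0.10, σ² = 0.959: 1 + 0.01 × 220 × 0.284 × 0.716 / 0.959 = 1.47, so size ≈ 10.6%, and the printed standard error should be √1.47 = 1.21 times larger. With σ² = 0.480 the ratio is 1.93 and the size 15.9%. By this formula a 10% error for FSM needs τ of about 0.07-0.10, and 25% needs about 0.14-0.20.

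**Simulation.** A random-intercept REML fit, true interaction zero, varying school sizes, 1,500 runs per cell (1,000 for the omnibus). Ranges run over the two baseline assumptions.

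| Gap SD τ | FSM | SEND/EHCP | Mixed (single contrast) |
|---|---|---|---|
| 0 | 4.4-5.7% | 4.3-5.0% | 4.6-5.5% |
| 0.05 | 7.1-8.3% | 5.5-6.4% | 5.3-5.6% |
| 0.10 | 11.7-19.3% | 10.5-13.8% | 7.3-7.7% |
| 0.15 | 19.4-28.9% | 14.0-21.8% | 9.4-13.1% |
| 0.20 | 28.0-41.3% | 19.8-31.1% | 11.3-18.3% |

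These mostly lie somewhat above the formula, as expected with unequal schools. Multiplying the FSM excess by 1 + 0.366² = 1.134 gives 11.3% and 17.2% at τ = 0.10. Monte Carlo error is about √(0.05 × 0.95 / 1500) = 0.6 percentage points near 5%.

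The five-degree-of-freedom ethnicity omnibus gave 6-10% at τ = 0.05 and 13-27% at 0.10. This needs two further assumptions: how ethnic groups cluster by school, and that all five gaps vary independently with the same SD.

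**With gap variation allowed for.** Weighting school-level gaps with τ² in the weights and testing on about 60 degrees of freedom gave 4.0-5.7% in every FSM, SEND/EHCP and Mixed scenario.

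**The case against.** The strongest reply is that the size is unknown. At a gap SD of zero there is no error, and at 0.05 it is about 1.1 to 1.7 times nominal for FSM and SEND/EHCP. A reader might infer from the larger rows that these tests run at two to five times their nominal error. The document does not support that as a statement of fact: for FSM and SEND/EHCP it needs a gap SD of roughly 0.10-0.20, half to all of the school-intercept SD, and nothing in the SAP says gaps vary that much. This objection stands.

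Second, the upper ends of the ranges cut the residual variance for baseline adjustment but leave the gap variance untouched, although the baseline score may also absorb stable gap differences. If both were halved, the ratio would be as without adjustment: about 11%, 17% and 25% for FSM at 0.10, 0.15 and 0.20 by the formula. This stands as a reason to read the upper ends with care. Fewer pupils also lower the figures: with 165 per school (220 × 0.75), FSM at 0.10 gives 9.2-13.3% by the formula.

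Third, the interactions are labelled exploratory and are not to be interpreted individually. That limits the harm, but it does not make the standard errors or intervals right.

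Fourth, a reader might extend the point to staff ethnicity. With about 26 staff per school and 280 of 1,620 staff Asian (17.3%), the ratio at τ = 0.10 is 1.04-1.08 and the size about 5.4-5.9%. The extension is not warranted.

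Fifth, the primary random-effects structure is itself inconsistent across text, syntax and equation. That must be settled first, but none of the three readings supplies the missing slope.

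**Conclusion.** The point holds in conditional form. The SAP tests group by FSM, SEND/EHCP and pupil ethnicity against within-school error only, in a school-randomised trial, and neither FDR adjustment nor the exploratory label corrects the resulting p-values and intervals.

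How far the error exceeds 5% depends on a between-school gap SD that the SAP does not state. It ranges from no inflation at zero, through a modest excess at 0.05, to roughly two to four times nominal for FSM at 0.10. It is lower for SEND/EHCP, lower still for single contrasts in small ethnic groups, and possibly higher for the ethnicity omnibus. These figures assume 220 pupils per school at follow-up and baseline explaining 0 to 50% of the variance. Severity is minor, because the analyses are exploratory; the change is worth making because it is cheap.

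**What to change.** First reconcile the random-effects structure of the primary model across text, syntax and equation, since the subgroup models inherit it. Then:

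- For each binary pupil moderator, add a school-level random slope correlated with the intercept, e.g. `(1 + FSM | school)` and `(1 + SEND | school)`, and test the interaction on school-level degrees of freedom (about 60 with 62 schools). The slope should not be forced to be uncorrelated with the intercept: that would make the result depend on which category is coded 1 and would force that category to have the larger between-school variance.
- For the ethnicity omnibus test, pre-specify school-clustered robust standard errors with a small-sample correction. Five slopes with small categories are likely to give singular fits, and a method chosen in advance is better than one triggered by non-convergence.
- Leave the staff ethnicity models as they are.

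The cost is a few lines of SAP wording and one term, or one variance estimator, per exploratory model; no new data are needed. The downside is somewhat wider intervals on the interactions.

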### **Further analyses**

A longitudinal mediation analysis will be conducted to test whether safe social connections with teachers measured by the Student Engagement Instrument mediates the relationship between group allocation and externalising difficulties, accounting for pupils nested within schools and repeated pupil measurements over time. For the mediation model, the package *lavaan* (version 0.6-17) in R will be used (Rosseel, 2012). This will be an exploratory analysis that may be used to drive future research.

To explore the impact of imbalance at baseline in staff-reported ARTIC-35 subscales (see Table 1), an additional model will be run that includes baseline school-level ARTIC-35 subscale scores as a control variable in the main analysis with pupil externalising symptoms as the outcome variable.

### **Interim analyses and stopping rules**

Reports will be prepared in March 2024 for the Data Monitoring and Ethics Committee (DMEC) covering recruitment and adverse events as part of monitoring of trial progress. However, no formal interim analysis considering either efficacy or futility will be undertaken. Stopping rules were not specified in the protocol and recruitment targets were met based on a priori power calculations. As a result, the only stopping rules will be where the DMEC makes a recommendation for the trial to terminate early based on safety concerns. We will continue to monitor withdrawals and assess study continuation from that. For example, a priori power calculations found that a minimum of 36 schools total is needed for a MDES of 0.20, which is the Youth Endowment Fund's MDES requirement.

### **Longitudinal follow-up analyses**

There are two follow-up points planned: mid-programme (cohort 1: April 2024; cohort 2: July 2024) and end of programme (cohort 1: March 2025; cohort 2: June 2025). All outcome

measures specified previously will be included. The analytical models specified previously incorporate the longitudinal follow-up data.

After the end of the YEF-funded study (winter 2025), Anna Freud will link the quantitative data on pupils to national data from the National Pupil Database through the Office for National Statistics Secure Research Service. This will enable us to examine longer-term impacts of the programme on attendance, exclusions, and permanent exclusions. As this is beyond the timeframes of the present study, it will be conducted as non-costed work by Anna Freud, with the intention of submitting a peer-review journal article. Longer-term analyses will also be conducted by YEF as part of the YEF Data Archive.

### **Imbalance at baseline**

Table 1 provides baseline descriptive statistics for intervention and control groups, as well as the p-values for the t-tests for continuous data and chi-square tests (post-hoc test p-values in brackets) for count data. Members of the research team who are unblinded to intervention group allocation have access to the data in this table.

The school-level percentage of pupils eligible for free school meals and percentage of pupils with SEND or EHCP status was acquired through public data and averaged for intervention and control schools.

The pupil and staff descriptive statistics are from the baseline self-report pupil and staff surveys. Data from participants who had complete primary outcome data available (SDQ externalising for pupils and ARTIC-35 for staff) are included in the table. Please note that data on year group (year 8 or year 9) is currently only available for cohort 2 schools. Year group data for cohort 1 pupils is shown as missing and will be obtained from the school administrative data in July 2024.

In terms of imbalance at baseline, there are more females and less males in the intervention schools compared to control schools. This can be explained by a higher proportion of boys' schools present in the control group. Furthermore, intervention schools had a higher mean score on three out of the five ARTIC-35 sub-scales (Response to Problem Behaviour, On the Job Behaviour (Empathy and Control) and Reactions to Work) compared to control schools. This indicates that staff in the intervention schools have greater alignment with trauma-informed practice beliefs in those areas compared to the control schools. This may be partially explained by the differences in the staff response rate between intervention and control

schools (intervention: 35.1%, n = 29 schools; control: 28.3%, n = 28 schools). Please note that the response rates do not include schools who have not yet provided total school staff numbers; two are missing in the intervention arm, and three in the control arm.

Table 1. Baseline descriptive statistics of schools, pupils, and staff at baseline, split by intervention and control group.

	Intervention group (n = 31 schools)	Control group (n = 31 schools)	p
School-level	Mean (SD)	Mean (SD)	
Percentage of pupils with FSM eligibility	28.6% (10.6%)	28.2% (13.5%)	0.89
Percentage of pupils with SEND/EHCP status	15.6% (4.5%)	16.5% (4.6%)	0.41
Pupils	Mean (SD)	Mean (SD)	
SDQ Externalising Symptoms	7.58 (4.24), n = 6429	7.52 (4.22), n = 7194	0.41
Year group (Cohort 2 only)	Count (%)	Count (%)	0.25
Year 8	2659 (41.4%)	2822 (39.2%)	
Year 9	2518 (39.2%)	2796 (38.9%)	
Missing	1252 (19.5%)	1576 (21.9%)	
Gender			<.001

	Intervention group (n = 31 schools)	Control group (n = 31 schools)	p
Female	3151 (49.0%)	3224 (44.8%)	(<.001)
Male	2978 (46.3%)	3668 (51.0%)	(<.001)
Non-binary	51 (0.8%)	64 (0.9%)	
Questioning	46 (0.7%)	52 (0.7%)	
Other	58 (0.9%)	59 (0.8%)	
Prefer not to say	145 (2.3%)	127 (1.8%)	
Ethnicity			0.13
Asian/Asian British	1492 (23.2%)	1753 (24.4%)	
Black/African/ Caribbean/Black British	398 (6.2%)	426 (5.9%)	
Mixed/Multiple ethnic groups	267 (4.2%)	346 (4.8%)	
Other ethnic group	244 (3.8%)	270 (3.8%)	
White	3699 (57.5%)	4074 (56.6%)	
Prefer not to say	329 (5.1%)	325 (4.5%)	
Staff			
ARTIC-35 sub-scales	Mean (SD), n = 724	Mean (SD), n = 896	

	Intervention group	Control group	p
	(n = 31 schools)	(n = 31 schools)	
Underlying Causes	4.75 (0.76)	4.67 (0.77)	0.04
Response to Problem Behaviour	5.05 (0.82)	4.90 (0.86)	<0.01
On Job Behaviour (Empathy and Control)	5.22 (0.75)	5.14 (0.74)	0.02
Self-Efficacy at Work	5.30 (0.92)	5.25 (0.94)	0.21
Reactions to Work	5.06 (0.78)	4.96 (0.84)	0.02
Gender	Count (%)	Count (%)	0.36
Female	515 (71.1%)	610 (68.1%)	
Male	206 (28.5%)	280 (31.3%)	
Non-binary	0 (0%)	0 (0%)	
Questioning	1 (0.1%)	0 (0%)	
Other	0 (0%)	1 (0.1%)	
Prefer not to say	2 (0.3%)	5 (0.6%)	
Ethnicity			0.26
Asian/Asian British	120 (16.6%)	160 (17.9%)	
Black/African/Caribbean/Black British	24 (3.3%)	16 (1.8%)	

	Intervention group (n = 31 schools)	Control group (n = 31 schools)	p
Mixed/Multiple ethnic groups	13 (1.8%)	17 (1.9%)	
Other ethnic group	20 (2.8%)	15 (1.7%)	
White	539 (74.4%)	677 (75.6%)	
Prefer not to say	8 (1.1%)	11 (1.2%)	

Note: ARTIC-35 = Attitudes Related to Trauma-Informed Care-35, EHCP = Education, Health and Care Plan, FSM = free school meals, SEND = special education needs and disabilities, SDQ = Strengths and Difficulties Questionnaire.

### **Missing data**

We will explore the amount of missingness in the data, such as the percentage of missing values per variable. We will evaluate the extent to which data are systematically missing by investigating which baseline variables are associated with missingness for the primary outcome of externalising symptoms at the end of programme time point. Multi-level logistic regression will be conducted to identify variables that predict missingness (0 = not missing, 1 = missing).

Intervention schools that have withdrawn post-randomisation will still be asked to participate in the follow-up data collection periods, to minimize missing data and the need for imputation.

We will have two approaches to addressing missing data and we will compare the results between approaches:

- 1) Multiple imputation will be conducted for any baseline and follow up data. Data will be imputed with data in wide format without clustering for time, as time will be included as a dummy coded variable in the analysis. The package *mice* will be used to impute missing values (van Buuren & Groothuis-Oudshoorn, 2011). The quickpred

function within mice will be used with a minimum correlation of 0.25 to build the predictor matrix for imputation. School will also be specified as a predictor in the predictor matrix. At least 25 imputations will be specified; the number of imputations will match the percentage of missing data. Analyses will be run with these datasets with the pooled estimates derived.

- 2) Participants with at least one post-randomisation datapoint (i.e. mid-programme or end of programme) will be included and analyses will be run with maximum likelihood estimation.

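### The multiple-imputation rule does not force in group allocation or the other analysis-model terms, so that estimate may be diluted, depending on how school is entered

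*SAP*

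**What the plan says.** The SAP plans two approaches to missing data and will compare their results.

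- **Multiple imputation (Missing data, item 1).** "Multiple imputation will be conducted for any baseline and follow up data". The layout is wide: "Data will be imputed with data in wide format without clustering for time". Predictors are chosen by correlation, since the quickpred "function within mice will be used with a minimum correlation of 0.25 to build the predictor matrix for imputation". One variable is added regardless of the screen: "School will also be specified as a predictor in the predictor matrix". Group allocation is not named, nor are cohort, year group, gender or LA/CA. The SAP does not say whether school enters as a factor, a numeric code or a cluster identifier.
- **Maximum likelihood (Missing data, item 2).** "Participants with at least one post-randomisation datapoint (i.e. mid-programme or end of programme) will be included".

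The model fitted to the imputed data contains terms that the imputation rule does not protect: "Fixed effects will include group allocation (intervention/control), time (mid-programme/end of programme), and the interaction between group allocation and time", with cohort, year group, gender and (if estimable) LA/CA. It also adjusts for baseline: "The baseline level of the outcome will be included as a covariate to increase power and precision". The subgroup models add interactions of group with ethnicity, FSM and SEND/EHCP.

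**The concern.** An imputation model should contain every term of the model that will be fitted to the completed data. If allocation is missing from it, and nothing else carries the arm difference, missing outcomes are filled in as though the arms did not differ. The pooled estimate then moves towards no effect.

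A correlation threshold suits the choice of auxiliary variables. It does not suit the treatment indicator, because a balanced binary variable has a low correlation with the outcome even when the effect is worth detecting.

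The comparison of the two approaches is the SAP's check on missing data. If one of them omits the tested term, the two may disagree for a purely technical reason, and a reader may take the gap as evidence about the missingness.

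**Working it through.** **Inputs from the SAP.** Power command at randomisation: means 5.21 and 4.7, SD 2.96, ICC 0.041, 219.73 pupils per school, CV 0.366, power 0.8, two-sided alpha 0.05. Pupils at baseline: 6429 intervention, 7194 control, in 62 schools. Planning allowances: 25% pupil and 15% school attrition. Screen: 0.25.

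**Assumptions not in the SAP.** Correlation of 0.6 between any two time points (the SAP says evidence on the pre-post correlation is lacking); the same effect at both follow-ups; end scores missing at random; numeric school codes unrelated to arm.

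**1. The planned effect reproduces.** The effect is 0.51/2.96 = 0.172.
- Unclustered n per arm: 2 × (2.96 × 2.8016/0.51)² = 528.8.
- Design effect: 1 + 218.73 × 0.041 = 9.968.
- Unequal cluster sizes: L = 9.009/9.968 = 0.904, so relative efficiency = 1 − 0.366² × 0.904 × 0.096 = 0.988.
- Result: 528.8 × 9.968/0.988 ≈ 5333 pupils and 24.27 schools per arm; 24.27/0.85 = 28.6, rounded up to 29 schools and 6372 pupils, as the SAP states.

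**2. Allocation against the screen.** With p = 6429/13623 = 0.472, √(p(1−p)) = 0.499 and r = 0.499d/√(1 + 0.249d²).
- d = 0.15, 0.17, 0.20 give r = 0.075, 0.085, 0.099.
- r = 0.25 needs d = 0.25/(0.499 × √(1 − 0.0625)) = 0.52.

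If quickpred also keeps variables correlated with the missingness indicator, allocation passes that way only if the arms differ in missingness by 0.25 × √(q(1−q))/0.499. That is 18, 22 or 25 percentage points at q = 15%, 25% or 40% missing. Gender and year group face a similar hurdle of roughly 0.5 SD.

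**3. Share of the main effect kept.** Simulated: 62 schools of 220 pupils, ICC 0.041, true effect 0.17, 60 runs per scenario.

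| Missing end scores | Numeric code | Numeric code, mid score used | School factor (without / with mid score) |
|---|---|---|---|
| 15% of pupils | 86% | 91% | 101% / 99-100% |
| 25% of pupils | 75% | 84% | 100% / 100% |
| 40% of pupils | 60% | 75% | 99-100% / 99% |
| 25% of pupils, plus about 15% of schools | 64% | 77% | 84% / 90% |

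With allocation forced in, the share kept is within about 1% of 100% in every row. In the last row, 10 of 62 schools have no end-of-programme scores, and inestimable school levels are dropped. The figures that use the mid score suppose those schools did return it.

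**4. Arithmetic check and range.** Without the mid score, imputed values carry no arm difference, so the share kept is 1 − f, whatever the correlation. Here f is the fraction whose imputed values carry no arm information.
- Numeric code: f = 25% gives 75%. With schools lost, f = 1 − 0.75 × 52/62 = 37%, giving 63%.
- Factor: only the lost schools count, f = 10/62 = 16%, giving 84%.

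With the mid score, its coefficient given baseline is ρ/(1+ρ), which is 0.375 at ρ = 0.6. The share kept is then 1 − f(1 − 0.375). For ρ from 0.4 to 0.8:
- numeric code, 25% pupil loss: 82-86%;
- numeric code, schools also lost: 74-79%;
- factor, schools lost: 89-91%.

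**5. Subgroup interactions.** Best case for the SAP: school factor, no school lost, baseline as predictor. Assumed: subgroup prevalence 28.5%, true interaction 0.20 SD, subgroup and interaction absent from the imputation model. The interaction came out at 0.168, 0.151 and 0.119 at 15%, 25% and 40% missing, against 0.19-0.20 with the terms included. The 1 − f rule gives 0.17, 0.15 and 0.12.

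**The case against.** The strongest reply is that the SAP does force school in. Schools were randomised, so arm is constant within a school, and a school factor carries the arm contrast together with cohort and LA/CA. This stands. A reader might infer that the 0.25 rule necessarily dilutes the treatment effect. The SAP does not support that: with a school factor and some follow-up from every school, the main effect is fully kept.

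It is also fair that the 64% figure combines unfavourable conditions: a numeric code, which the SAP nowhere states; whole-school loss; and no mid-programme score. The 15% is a sample-size allowance, not a forecast. The SAP will still ask withdrawn intervention schools for follow-up, although it has no matching sentence for control schools. Wide-format imputation lets the mid-programme score help. The baseline score would be expected to pass the screen. The subgroup analyses are labelled exploratory.

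These points limit the size of the problem but do not remove it. The SAP leaves the coding of school open, does not say how wholly lost schools are imputed, and protects no within-school interaction.

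**Conclusion.** The point holds as a conditional one. At any effect the trial plans for, allocation is screened out of the imputation model, and probably gender and year group too. The interaction terms have no protection either. The multiple-imputation estimate may then be diluted:

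- by about a quarter at 25% pupil loss if school is a numeric code;
- by about 10-16% with a school factor if some 15% of schools return no end-of-programme data;
- not at all with a school factor and follow-up from every school.

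Group-by-subgroup interactions lose roughly the missing fraction under either coding when only baseline informs the imputation. Sizes that use the mid-programme score rest on the assumed correlation; the others depend mainly on the fraction missing.

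A reader might extend the criticism to the maximum-likelihood analysis. That would be wrong, because it does not use the predictor matrix. It has a separate wording fault. The Analysis section says "The analyses will use maximum likelihood estimation meaning all participants will be included, even those with missing follow up data points", yet the same section and Missing data restrict this approach to participants with a post-randomisation score. With baseline as a covariate, those without a baseline score drop out as well. This has no bearing on the dilution.

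**What to change.** In Missing data, item 1:

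- Use quickpred's include argument to force in group, the baseline, mid-programme and end-of-programme scores, cohort, year group, gender and LA/CA. Apply the 0.25 screen to auxiliary variables only.
- For the subgroup models, include the subgroup variable and its interaction with group, or impute separately by arm. Imputing by arm replaces group as a predictor, since group is then constant.
- State that school enters as a factor, or as the cluster identifier in a multilevel imputation with group as a predictor. Either would do: the calculations do not show that multilevel imputation is needed to remove this bias. Check that group remains estimable alongside school dummies, because arm is a linear combination of them.
- State how pupils and staff in wholly lost schools are imputed.

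Separately, in Analysis, replace the statement that all participants are included with one that the likelihood approach keeps those with a baseline score and at least one post-randomisation score. Moving baseline into the outcome vector is optional and not needed for this point.

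The cost is a few sentences and a few lines of code, with somewhat longer run time if multilevel imputation is chosen. No data collection changes.
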